- Oversee the work of the data clerk as below and assume any of the duties of the clerk that may be required due to his absence or inability to perform
- Manage the data clerk
- Contribute to the design and modification of protocols, which define what and when data are to be collected
- Design and approve forms on which data are collected
- Be responsible for data collection forms and informed consents (both old and new) that are used in the study
- Manage data information entered by the data clerk on study patients with Hope Center
- Ensure that patient study files are properly filled, documented, and stored
- Manage data backup on weekly basis
- Coordinate the transfer of data with the Coptic Hope data manager to the research databases with the data clerk
- Design SPSS database and manage both the SPSS and Access databases for the study
- Ensure the databases meet requirements for the entry and reporting of clinical data
- Maintain daily, weekly, and monthly work schedules for the data office with the data clerk and ensure their completion
- Check for errors in the data, correct the errors, and maintain cleanliness of the data
- Check and manage the data log book of errors produced by the data clerk
- Coordinate the data-checking process and produce a monthly report on the data quality

- Thoroughly clean the data every 3 months to ensure cleansing of errors
- Sort out any data entry or error problems weekly with the study doctor and study coordinator
- Run frequencies and range checks to identify extreme values monthly
- Present weekly and monthly reports of data analysis
- Assist the study doctor and receptionist in the presentation of weekly summaries marking progress in enrollment and tracking of subjects in the study
- Assist the receptionist and study doctor in the preparation of monthly summary tables on number of women enrolled in each study arm and to consolidate the weekly reports
- Prepare laboratory shipping lists with the lab technologist
- Be responsible for maintaining the security of the data
- Generate study ID numbers
- Be responsible for linking and de-linking data
- Train clinical research staff to help improve the quality of the data being collected
- Assist in standardizing data management procedures such as documentation for study operating procedures
- Develop and maintain documentation and data management guidelines
- Perform other duties that may be given by the principle investigator or study coordinator

Data Clerk

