 - Those with biopsy results that are positive for a high grade pre-cancerous lesion (CIN 2/3 or CIS) and if the lesion is amenable to cryotherapy or LEEP as per Kenyan national guidelines, will be eligible for randomization. If they are willing to undergo informed consent for the treatment study, they will be randomized to receive either cryotherapy or LEEP (see Study Flow II). Those who decline to participate in the treatment study will be exited and referred to KNH for treatment. Randomization questionnaire will also be completed during this visit.
 - Those patients who do not have lesions which are amenable to cryotherapy due to size or access will not be randomized but will be offered free LEEP and followed up every 6 months for 2 years, the same way as randomized participants. Those who have lesions that are neither amenable to LEEP nor cryotherapy due to size or severity of disease, or anatomy does not allow proper access to the cervix, will be referred to KNH for subsidized care at this government hospital. The study will not pay for this treatment. Patients will be given follow-up appointments in the study clinic after referral to determine outcomes. They will have the option to continue to be followed at the CCSP.

- Those with CIN 1 will not be randomized or exited but will be asked to return to the study clinic after 6 months for a repeat Pap smear.
- Those who show no dysplasia on histology will be exited from the study and referred to the CCSP for further follow-up.
- It is expected that approximately 400 patients will be eligible for randomization. During randomization, a sealed envelope will be opened by the study doctor that will reveal the randomization arm that has been assigned to the study ID number. Randomization assignment will be performed on a computer by [name], the study statistician, in Seattle, and preparation of the envelopes will be performed by the study data manager in Nairobi in conjunction with [name]. This is the standard used for all randomized clinical trials conducted by the University of Washington in Kenya. Study investigators and the study doctor will not have access to the randomization sequence. Study investigators and staff will not be blinded to randomization.
- Those eligible for randomization will have an HIV cervical viral level swab taken before treatment (LEEP or cryotherapy).

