are very high. It has long been known that HIV-positive women are at higher risk of cervical disease and faster progression of lesions.^{42, 43} From preliminary studies performed on our HIV-positive patient population, we have found that the prevalence of high-grade lesions is around 8% in women 30-39 years old and taking antiretroviral medications.⁴⁴ Additionally, studies have shown that either method of treatment is extremely effective in treating CIN.²⁷

E. CONFIDENTIALITY OF RESEARCH DATA

1. Will you record any direct subject identifiers (names, Social Security numbers, patient, hospital, laboratory or claim numbers, addresses, telephone numbers, locator information, etc.) No Yes If yes, explain why this is necessary and describe the coding system you will use to protect against disclosure.

We will be recording names and assigning a study number that will be used on all study visits. This is to ensure accurate follow-up of study participants. This will be handled by the senior data analyst.

2. Will you retain a link between study code numbers and direct identifiers after the data collection is complete? No Yes If yes, explain why this is necessary and for how long you will keep this link.

The link between the study participant's name and study number is necessary to facilitate follow-up during the 1 month study period. This link will no longer be needed after follow-up is completed and will be removed after 5

years. This will be handled by the senior data analyst. Data and specimens will be stored for 10 years after completion of study follow-up before being destroyed.

3. Describe how you will protect data against disclosure to the public or to other researchers or non-researchers. Explain who (other than members of the research team) will have access to data (e.g., sponsors, advisers, government agencies, etc.).

All names and numbers will remain in confidential files that are accessible only to the investigators and study staff. Computer databases containing information about study subjects will be protected by passwords which allow access to only the investigators.

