- authorized representatives of CDC (e.g., a contracted party considered to be “external”)
- both internal and external parties

Monitoring or auditing may be performed by means of on-site visits to the Investigator’s facilities or through other communications such as telephone calls or written correspondence. The visits will be scheduled at mutually agreeable times, and the frequency of visits will be at the discretion of CDC. During the visit, any study-related materials may be reviewed and the Investigator along with study staff should be available for discussion of findings.

The study may also be subject to inspection by regulatory authorities (national or foreign) as well as the IECs/IRBs to review compliance and regulatory requirements.

Acronyms

AIDS – Acquired Immunodeficiency Syndrome

CCSP – Cervical Cancer Screening Program, Coptic Hope Center for Infectious Diseases

CDC – Centers for Disease Control

CIN – Cervical Intraepithelial Neoplasia

CIS – Carcinoma in situ

CVL – Cervicovaginal Lavage

HIV – Human Immunodeficiency Virus

HPV – Human Papillomavirus

IRB – Institutional Review Board

KNH – Kenyatta National Hospital

LEEP – Loop Electrosurgical Excision Procedure

OGAC – Office of the Global AIDS Coordinator

Pap – Papanicolaou

PEPFAR – President’s Emergency Plan for AIDS Relief

PHE – Public Health Evaluation

RNA – Ribonucleic Acid

UNITID – University of Nairobi Institute of Tropical and Infectious Diseases

UoN – University of Nairobi

USA – United States of America

USG – United States Government

UW – University of Washington

VIA – Visual Inspection with Acetic Acid

ENROLLMENT

Study ID Number ___ ___ **Hope ID Number** ___ ___ **Interviewer Number** ___

Date of interview (day/month/year) ___ ___ / ___ ___ / ___ ___

Agreed to store samples: Yes No Don't know Other, specify

A: SOCIODEMOGRAPHIC

1. Date of birth (day/month/year) ___ ___ / ___ ___ / ___ ___

2. Age _____ years

3. How many years of education did you complete? _____ years

4. What is highest education level you have completed? None

Primary

Secondary

Higher education/ University

Don't know

Refused

Other, specify

5. Marital status (tick one): Married (monogamous)

Married (polygamous)

Single

Divorced/Separated

Widowed

Refused

Cohabiting

Other, specify

6. Employment (tick one): Salaried job

Self-employed

- Housewife
- Unemployed
- Casual laborer
- Refused
- Other, specify

7. Household income per month (tick one): None
- < 5000 Ksh

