- Polyp or anatomic defect preventing access to cervix
- Previous treatment with cryotherapy in this study
- Other, specify

22. What was your diagnosis based on colposcopy examination (tick all that apply)?

- Normal colposcopic findings
- Unsatisfactory, specify:
- Inflammation/infection, specify
- Leukoplakia
- Condyloma
- LSIL (CIN 1)
- HSIL (CIN 2 & 3)
- Invasive cancer
- Other, specify:

D: SPECIMEN COLLECTION

23. Was a biopsy taken? Yes No
- a. If yes, how many biopsies were taken ___
 - b. Draw: (mark site(s) with an 'X' on colposcopy drawing)
 - c. If no, specify why biopsy was not taken

E: Treatment

24. Was any treatment given to the patient? Yes No
If yes, specify treatment
25. Was a referral given to the patient? Yes No
If yes, specify diagnosis, and the referral institution

26. Comments:

RANDOMIZATION

Study ID Number _____ Hope ID Number _____

Randomization Number __ Interviewer Number _

Date of interview (day/month/year) ____/____/____

A: CURRENT MEDICAL HISTORY

1. Do you have pain when passing urine? Yes No Other, specify Refused Don't know
2. Do you have any lower abdominal pain? Yes No Other, specify Refused Don't know
3. Do you have any abnormal vaginal discharge? Yes No Other, specify Refused Don't know
4. Have you noticed any growths around your vagina? Yes No Don't know Other, specify Refused Don't know

B: REPRODUCTIVE HEALTH

5. How old were you when you had your first menstrual period? ____ Don't know refused Other, specify
6. Date of last menstrual period (day/month/year) ____/____/____ Don't know refused Other, specify
7. Do you have history of abnormal vaginal bleeding Yes No Don't know Refused Other, specify

If yes specify the type of bleeding

- Irregular
- Heavy
- Menorrhagia Other, specify
- Don't know
- Refused

8. Have you ever used any form of family planning method? Yes No
Don't know

Refused

Other, specify _____

If yes, specify (tick all that apply)

Injectable IUCD Natural

Condoms OCP Norplant/ Implant

BTL others, specify _____

9. Are you using any form of family planning method now?

Yes No Don't know Refused

Other, specify _____

If yes, specify (tick all that apply)

Injectable IUCD Natural

Condoms OCP Norplant/ Implant

BTL others, specify _____

10. How many times have you been pregnant? ___ ___ Refused Don't know
Other

11. How many times have you had live births? ___ ___ Refused Don't know
Other

12. How many abortions, miscarriages, and/or stillbirths have you had? ___ ___

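### Allocation concealment is not secured by the written procedure: the arm is tied to a study ID held since screening, and the no-access rule omits the data manager who prepares the envelopes

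*Combined protocol and SAP*

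**What the plan says.** In the combined protocol and SAP, Study Procedures, item 3 (the 6–8-week randomization visit), the study doctor opens a sealed envelope that will "reveal the randomization arm that has been assigned to the study ID number". The study statistician in Seattle produces the assignments by computer. Then "preparation of the envelopes will be performed by the study data manager in Nairobi", together with a second person whose name is removed from the public text. The safeguard reads: "Study investigators and the study doctor will not have access to the randomization sequence". Investigators and staff are not blinded to treatment.

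The Enrollment form, completed at screening, is headed with a "Study ID Number" field, and Ethics, section E, describes "assigning a study number that will be used on all study visits". One of the data manager's listed duties under Personnel is "Generate study ID numbers". Data Management (Safety, Security, & Storage) repeats this and makes the same person responsible for linking and de-linking data.

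The Randomization form carries a separate "Randomization Number" beside the study ID. The protocol text never says what that number does.

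**The concern.** Concealment means that nobody who influences whether a woman is randomised can know her arm beforehand. Here the study doctor confirms eligibility, performs colposcopy and treatment, and opens the envelope. If the arm belongs to an ID that has existed since screening, there is a period of weeks in which it could become known. The person on site who knows both the IDs and the envelope contents is outside the written prohibition.

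The outcome of the amenability judgement matters. A woman judged unsuitable for cryotherapy is not randomised. She is offered free LEEP and followed every 6 months, but outside the randomised comparison. If that judgement were influenced by a known arm, the two arms would differ in lesion severity from the start. Intent-to-treat analysis protects only against what happens after randomisation.

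**Working it through.** The plan states no figure on this point, so the check is to set the passages side by side.

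**Timing**

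1. Screening (at least 2,400 women): Enrollment form completed, study ID in use.
2. From the two-week results visit: colposcopy and biopsy where indicated. Colposcopy form Q21 records cryotherapy eligibility, with reasons.
3. Four to six weeks after biopsy: histology result, treatment consent, Treatment form Q5 (amenable to cryotherapy?), then Q6 (randomised, and to which arm?). About 400 women reach randomisation.

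If the study ID carries the arm, the arm exists from step 1. If the Randomization Number carries it, the arm need not be attached to a woman until the end of step 3. Study Procedures states the first; the Randomization form suggests that the second may have been intended. The two must be reconciled.

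**Who can know the arm**

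- Seattle statistician: generates the assignments, away from recruitment.
- Data manager: generates the IDs and prepares the envelopes, so can hold both halves of the link. Not named in the no-access rule.
- Second person at envelope preparation: role not visible in the public text.
- Investigators and study doctor: barred from the sequence.
- Nurses, receptionist and other clinic staff: not named.

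**Contact.** The data manager's duties include settling data problems weekly with the study doctor and coordinator. The study doctor's duties include working with the data manager on analyses and reports. This is ordinary contact. It shows a possible channel, not a leak.

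**Route out of randomisation.** A *no* at Treatment form Q5, with the lesion treatable by LEEP, skips Q6 and goes to treatment at Q7. The accepted reasons include the patient declining the procedure and a free-text entry. Nothing says what happens if Q5 disagrees with the earlier Q21.

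**Not stated.** Opaque envelopes, serial numbering, custody and an opening log.

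**Size.** Suppose a share *f* of eligible women, with recurrence *h* after cryotherapy, were diverted whenever their arm was cryotherapy. The planned cryotherapy rate of 14% would become (0.14 − *f·h*)/(1 − *f*). Neither *f* nor *h* is in the documents, and *f* is zero if nothing leaks. No figure can be supported.

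**The case against.** The strongest reply is that assigning an arm in advance does not disclose it. The list is made in Seattle, the envelopes are sealed, a second person takes part in preparing them, and the doctor who judges amenability is expressly barred from the sequence. The data office is at KNH, away from the clinic. Eligibility is recorded at colposcopy and again before randomisation, against listed criteria for lesion size, visibility and access, so a late change of mind would leave a trace. The assistant study coordinator verifies randomization procedures, and unpublished SOPs may supply missing detail. Most of this stands, and it is why the point is one of incomplete protection. It does not remove the gap in the no-access rule or settle which number carries the arm.

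Five stronger readings are tempting but unsupported:

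- *Allocation is not concealed.* A reader might infer this, but it would need a leak, and the documents show none.
- *The study doctor controls consent.* Consent is listed among the nurses' duties; elsewhere the text says only study staff.
- *Monthly tables by arm reveal the next allocation.* The data manager does help with "preparation of monthly summary tables on number of women enrolled in each study arm", but these describe women already allocated. They would help prediction only with known small blocks filled in order, and no blocking is stated.
- *Tying arms to screening IDs spoils block balance.* No block design is stated to spoil. Even if 2,400 IDs were assigned 1:1 (an assumption) and 400 used, the SD of one arm's size would be √(400 × 0.25 × 2,000/2,399) ≈ 9.1. Power for 4% versus 14% after 20% loss would be about 0.875 at a 180:220 split, against 0.882 at 200:200.
- *The comparison is biased by a calculable amount.* Any such number rests wholly on assumed inputs.

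**Conclusion.** The point holds as a weakness in the written procedure. As worded, the arm is tied to an identifier that exists before amenability is judged and treatment consent is sought. The local role that generates that identifier and prepares the envelopes falls outside the no-access rule. The exposure is a leak of a particular woman's arm before the amenability decision, which could move her to non-randomised LEEP.

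This rests on reading Study Procedures literally. If the Randomization Number in fact carries the arm and is issued at randomisation, the timing problem falls away, while the gap in the no-access rule remains. Disclosure is not shown, and the size of any bias cannot be estimated from the documents. The change is worth making because it is cheap and selection before randomisation cannot be repaired in the analysis.

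**What to change.** Amend Study Procedures, item 3, and the matching SOP:

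- State that the arm is carried by the sequential Randomization Number already on the Randomization form, not by the screening study ID.
- Issue that number only once the Treatment form Q5 answer, checked against Colposcopy form Q21, and the signed treatment consent are recorded.
- Have the Seattle statistician's office prepare and seal opaque, serially numbered envelopes and hold the only list.
- Have the study ID, date and time written on each envelope before it is opened.
- Extend the no-access rule to the data manager and all clinic staff.

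The cost is a small courier charge and SOP revision. No clinical criterion changes, and the monthly enrolment tables can stay as they are.
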